9. RESPONSE EVALUATIONS AND MEASUREMENTS

Response and progression will be evaluated in this study using the International Myeloma Working Group Uniform Response Criteria (see Appendix E).

CR	Complete Response
sCR	subcategory: stringent complete response
VGPR	Very good partial response
PR	Partial response
SD	Stable disease
PD	Progressive disease

All response categories (CR, sCR, VGPR, PR, PD) require two consecutive assessments made at any time before the institution of any new therapy, as well as no known evidence of progressive or new bone lesions if radiographic studies were performed. Radiographic studies are not required to satisfy these response requirements. Bone marrow assessments are not required to be confirmed by repeat testing.

Complete response should be confirmed with a bone marrow biopsy for morphology and a bone marrow aspiration for flow cytometry, FISH, and cytogenetics performed locally. Additional confirmatory studies include SPEP, UPEP, immunofixation of blood and urine, and SFLC (see Appendix D).

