10.4.2 Efficacy Analysis

- PFS, defined as the time from the first day of study drug administration (Day 1) to disease progression as defined by the International Myeloma Working Group Uniform Response Criteria (see Appendix E), or death on study. Patients who are alive and free from disease progression will be censored at the date of last tumor assessment.
- OS, defined as the time from the first day of study drug administration (Day 1) or death on study. Patients who are alive will be censored at the date of last known date alive.

Progression-free survival and OS (efficacy secondary endpoints) estimates will be generated using Kaplan-Meier methods, both for all patients enrolled and those patients receiving the MTD. Two-year PFS and OS estimates with 95% confidence intervals (CIs), and median PFS and OS with 95% CIs, will be generated and reported accordingly.

The effect of MLN9708 on immune effector cells after allogeneic stem cell transplant will be analyzed by examining the difference in the actual change from baseline at Cycle 1 Day 4, Cycle 1 Day 8, Cycle 1 Day 15, and Cycle 2 Day 1, and the percentage change from baseline at Cycle 1 Day 4, Cycle 1 Day 8, Cycle 1 Day 15, and Cycle 2 Day 1, among those patients participating in the biomarker research component. Each analysis will be performed within dose level and total patients.

The following parameters will be examined:

- CD3+, CD4+, CD8+, CD45+, CD19+ and CD56+/CD16+ cell counts, by fluorescence-activated cell sorting
- Regulatory T cell counts by intracellular staining of FoxP3, and surface staining of CD4+ and CD25+ cells
- Inflammatory cytokine concentrations of IL-1 β , IL-6, IL-8, IL-10 and TNF- α .

CONFIDENTIAL

STUDY DRUG: MLN9708

SCRI INNOVATIONS STUDY NUMBER: MM 42

FINAL PROTOCOL: 11 APRIL 2014

AMENDMENT NUMBER 3: 11 FEBRUARY 2016

VERSION 4

For each parameter, the actual change from baseline and the percentage change from baseline, at each time point, will be analyzed using the two-sided Wilcoxon signed-rank procedure to test whether either the change is statistically different from zero.

The significance level will be set at 10%, and there will be no adjustment to the alpha level for multiple comparisons. The rationale for the reporting of p-values in these analyses is for hypothesis-generating purposes only.

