SCRI INNOVATIONS STUDY NUMBER: MM 42

VERSION 4

Appendix E: International Myeloma Working Group Uniform Response Criteria: Complete Response and Other Response Categories (continuation)

SD	Not meeting criteria for sCR, CR, VGPR, PR or PD
PD Progressive Disease	
Increase of $\geq 25\%$ from the nadir in at least one of the following criteria:
 
 • serum M-protein (absolute increase must be ≥ 0.5 g/dL and absolute value must be ≥ 1 g/dL) • urine M-protein (absolute increase must be ≥ 200 mg/24h) • only in patients with non-measurable serum and urine M-protein levels: difference in involved and uninvolved FLC levels (absolute increase must be >10 mg/L) • Bone marrow plasma cell percentage (absolute % must be $\geq 10\%$) 
OR
 
 • development of new lytic bone lesions or increase from baseline in size of lytic bone lesion(s) 
OR
 
 • development of new soft tissue plasmacytoma(s) or definite increase from nadir in existing soft tissue plasmacytomas 
OR
 
 • development of hypercalcemia (corrected serum calcium >11.5 mg/dL) for patients without hypercalcemia at baseline. In case of preexisting hypercalcemia at baseline, PD will only be assessed due to the hypercalcemia criterion in case the corrected serum calcium level was ≤ 11.5 mg/dL post-baseline and increased thereafter beyond 11.5 mg/dL.

^aAll response categories require two consecutive assessments made at any time before the institution of any new therapy; all categories also require no known evidence of progressive or new bone lesions if radiographic studies were performed. Radiographic studies are not required to satisfy these response requirements.

^bConfirmation with repeat bone marrow biopsy not needed.

Source: Kyle RA and Rajkumar SV Criteria for diagnosis, staging, risk stratification and response assessment of multiple myeloma. Leukemia 2009. 23:3-9

CONFIDENTIAL

SCRI INNOVATIONS STUDY NUMBER: MM 42

STUDY DRUG: MLN9708

FINAL PROTOCOL: 11 APRIL 2014

AMENDMENT NUMBER 3: 11 FEBRUARY 2016

VERSION 4

Appendix F: National Institutes of Health Consensus Development Project on Criteria for Clinical Trials in Acute and Chronic Graft-Versus-Host Disease

Organ Staging of Acute GVHD

Stage	Skin	Liver	GI tract
Organ staging 0	No rash due to GvHD	Bilirubin < 2 mg/dl or 35 µmol/l	None

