Definition of Endpoints:	Start Date:  Date of Randomization  Date of First Treatment End Date (specify for all pertinent endpoints): Progression-Free Survival: Event = Progression or Death 
  
 Situation	Date of Event or Censoring	Outcome	
   
 No baseline assessment	Date of first treatment	Censored	
 
 PD documented between scheduled visits, did not die, and received no subsequent therapy	First date of evaluated overall response = PD	Event	
 
 PD documented between scheduled visits, did not die, but received subsequent therapy prior to incurring progression event	Date of last evaluable tumor assessment prior to start of subsequent therapy	Censored	
 
 Death while on-study without previous PD, and received no subsequent therapy	Date of death	Event	
 
 Death while on-study and had previous PD, and received no subsequent therapy	First date of evaluated overall response = PD	Event	
  
	Situation	Date of Event or Censoring	Outcome	No baseline assessment	Date of first treatment	Censored	PD documented between scheduled visits, did not die, and received no subsequent therapy	First date of evaluated overall response = PD	Event	PD documented between scheduled visits, did not die, but received subsequent therapy prior to incurring progression event	Date of last evaluable tumor assessment prior to start of subsequent therapy	Censored	Death while on-study without previous PD, and received no subsequent therapy	Date of death	Event	Death while on-study and had previous PD, and received no subsequent therapy	First date of evaluated overall response = PD	Event
Situation	Date of Event or Censoring	Outcome																	
No baseline assessment	Date of first treatment	Censored																	
PD documented between scheduled visits, did not die, and received no subsequent therapy	First date of evaluated overall response = PD	Event																	
PD documented between scheduled visits, did not die, but received subsequent therapy prior to incurring progression event	Date of last evaluable tumor assessment prior to start of subsequent therapy	Censored																	

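### Section 9 and Appendix E footnote a rule out PD when bone lesions are known to have progressed, while the Appendix E PD row makes those same lesions PD

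*Protocol*

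**What the plan says.** Three statements in the protocol deal with bone lesions and response category.

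- **Section 9.** "All response categories (CR, sCR, VGPR, PR, PD) require two consecutive assessments made at any time before the institution of any new therapy", followed in the same sentence by "as well as no known evidence of progressive or new bone lesions if radiographic studies were performed". PD is named in the list and SD is not.
- **Appendix E, footnote a.** "all categories also require no known evidence of progressive or new bone lesions if radiographic studies were performed".
- **Appendix E, PD row.** One of the alternatives joined by OR is "development of new lytic bone lesions or increase from baseline in size of lytic bone lesion(s". No other finding is needed.

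SD is defined in Appendix E by exclusion: "Not meeting criteria for sCR, CR, VGPR, PR or PD".

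Protocol Section 10.4.2 defines PFS as time from first dose to progression by the Appendix E criteria, or death on study. SAP Section 5/6 takes progression as the investigator reports it. Its PFS table dates the event at "First date of evaluated overall response = PD" and has no line on confirmation. Under protocol Section 7.4, patients with PD come off, while those with SD or a response stay on treatment for the planned six cycles.

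**The concern.** One radiographic finding both establishes PD and disqualifies it, depending on which sentence the reader applies. A clause that makes sense for the response categories (a patient should not be called a responder while bone disease is advancing) has been attached to PD as well.

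Two-year PFS is a stated secondary objective, and SAP Tables 10 and 11 report response by the same criteria. If a site applies Section 9 as written, a skeletal progression is not an event when it is seen. The patient stays in the PFS risk set and may be reported as SD.

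A second inconsistency sits in the same Section 9 sentence. It requires two consecutive assessments for PD before any new therapy, whereas the SAP dates PD at the first report and does not say whether a second is needed. The protocol and SAP therefore do not share one rule for when PD is confirmed and how it is dated.

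**Working it through.** The plan gives no figure to reproduce, so the main check is to apply each rule literally to one patient with a known new or enlarging lytic lesion on a radiograph.

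| Rule | Application | Result |
|---|---|---|
| Section 9, with the Appendix E SD row | Bone-lesion condition fails for CR, sCR, VGPR, PR and PD. SD is not in the list and is whatever remains. | SD |
| Appendix E footnote a, taken as every category | Condition fails for every category, SD included. | No category |
| Appendix E PD row | Skeletal criterion met; it suffices alone. | PD |

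The three rules give three different answers. Under Section 9 the condition covers the PD category as a whole, so it would also block a PD based on M-protein if a new lesion were known at the same time.

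**Direction for PFS.** Where the literal Section 9 reading is followed, a true progression is not counted when it occurs. The patient either has a later event or is censored. Neither can lower the PFS estimate, so any bias is upward.

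**Scale per missed event (illustration).** The inputs are 38 patients (protocol synopsis) and complete 2-year follow-up (my assumption). The documents give no frequency of skeletal progression.

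- If the patient is counted as event-free at 2 years, crude PFS rises by 1/38 = 2.6 points. Two such patients give 2/38 = 5.3 points, and three give 3/38 = 7.9 points.
- If the patient is instead censored when r patients (this one included) are at risk, and m patients are truly event-free at 2 years, Kaplan-Meier PFS goes from m/38 to (r/38) × m/(r − 1). The rise is m/[38(r − 1)], which cannot exceed 1/38 because m ≤ r − 1.
- If the patient has a later counted event within 2 years, 2-year PFS in the crude calculation is unchanged and only the event time moves.
- For patients at the MTD, taking 6 from escalation plus 20 from expansion, the step is 1/26 = 3.8 points.

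**Confirmation and dating.** Section 9 sets no interval between the two assessments, only that both precede new therapy. The SAP PFS table treats the first PD report as the event, but censors at the last evaluable assessment before new therapy if that therapy came before the progression event. Take a patient with one PD assessment who starts new therapy before a repeat. If the Section 9 requirement is binding, there is no PD and the patient is censored. If the first report suffices, the patient has an event. The documents do not say which applies.

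**The case against.** The strongest reply is that Section 9 opens by making Appendix E the governing criteria, that PFS cites Appendix E rather than the Section 9 sentence, and that the SAP uses the investigator's call. An investigator who reads the PD row would record PD. Section 5.3.2 points the same way, since it treats a need for local radiation as generally a sign of progression. The clause also applies only if radiographs were taken, and Appendix D repeats the skeletal survey only when clinically indicated.

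Much of this stands. A reader might infer that a patient with skeletal progression can never be PD and is always scored SD. The documents do not support that: it holds only if Section 9 overrides the PD row, and footnote a taken literally would exclude SD too. What does not stand is that deferring to Appendix E settles the matter, because footnote a puts the conflict inside Appendix E. Footnote a alone might be read as covering only sCR to PR, but Section 9 closes off that reading by naming PD. As for imaging only when indicated, the example given is bone pain, so it would tend to be done in the patients to whom the conflict applies.

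A reader might also infer that the two-assessment requirement cannot be met because no second assessment is scheduled once PD is seen on treatment. That is not supported either. Section 7.5 names progression as a reason for stopping early and schedules a disease assessment 30 days after early discontinuation. Dating PD at the first report is, moreover, compatible with later confirmation. What remains is that the SAP is silent on whether confirmation is required.

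**Conclusion.** The contradiction is real and lies in the definition of a PFS event. Section 9 and footnote a, as written, exclude from PD a finding that the PD row makes sufficient for PD. If sites follow the literal wording, progressions can be left out of PFS and misreported in best response, and PFS is biased upward.

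The size is unknown. It depends on how often skeletal progression occurs and is imaged, and on how many investigators follow Section 9 rather than the PD row; the documents give none of these. The only defensible scale is per event: at most 2.6 points of 2-year PFS for each missed progression, assuming 38 patients with complete follow-up. The step is larger in a smaller analysis set.

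This is a moderate point. The protocol's primary objectives are MTD and safety, which it does not touch, and the protocol treats PFS as a secondary, single-arm, descriptive estimate with no test. It still merits correction, because PD also decides who leaves treatment under Section 7.4 and the change is small.

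**What to change.** 1. In Section 9 and in Appendix E footnote a, limit the condition on progressive or new bone lesions to sCR, CR, VGPR and PR, and take PD out of it. The PD row can stay as it is.
2. Reconcile the Section 9 two-assessment requirement for PD with the SAP PFS table. Both documents should state one rule covering whether PD needs confirmation, which date is used, and how a single PD assessment followed by new therapy or death is handled. The choice is the sponsor's. Because PD also governs discontinuation of treatment, Sections 7.4 and 9, Appendix E and the SAP must agree.

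The first item is a wording change in two places. The second is a few lines in the protocol and the SAP table. Neither in itself adds visits.

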10. STATISTICAL CONSIDERATIONS

10.1 Statistical Design

This is an open-label, multicenter, non-randomized study to determine the feasibility of MLN9708 as maintenance after allogeneic stem cell transplant for multiple myeloma. Patients will be enrolled between Days 45 and 120 after allogeneic transplant and will receive MLN9708 on Days 1, 8, and 15 of each 28-day cycle for 6 cycles.

10.2 Sample Size Considerations

For the dose-escalation phase of the study, a minimum of 2 and a maximum of 6 patients will be enrolled in each of 3 cohorts. Therefore, the maximum number of patients to determine the MTD will be 18. When the MTD is determined, an additional 20 patients will be enrolled in the expansion phase at either the MTD or the MPD.

10.3 Analysis Population

The following analysis populations will be used:

- The Safety population will consist of all patients who received at least one dose of MLN9708. This population will be used in all safety summaries.
- The Efficacy Evaluable population will consist of all patients with measurable or evaluable disease at baseline who receive at least 1 dose of MLN9708 and undergo at least one post-baseline disease assessment. In addition, patients who discontinued the study prior to their first post-baseline disease assessment due to death or progressive disease will also be included in the Efficacy Evaluable population.

10.4 Data Analysis

Descriptive statistics, including mean, median, standard deviations and ranges for all continuous measures will be tabulated and reported. Percentages and frequencies for all categorical measures will also be presented.

10.4.1 Demographics and Baseline Characteristics

Demographic data and baseline disease characteristics will be summarized using descriptive statistics.

10.4.2 Efficacy Analysis

- PFS, defined as the time from the first day of study drug administration (Day 1) to disease progression as defined by the International Myeloma Working Group Uniform Response Criteria (see Appendix E), or death on study. Patients who are alive and free from disease progression will be censored at the date of last tumor assessment.
- OS, defined as the time from the first day of study drug administration (Day 1) or death on study. Patients who are alive will be censored at the date of last known date alive.

Progression-free survival and OS (efficacy secondary endpoints) estimates will be generated using Kaplan-Meier methods, both for all patients enrolled and those patients receiving the MTD. Two-year PFS and OS estimates with 95% confidence intervals (CIs), and median PFS and OS with 95% CIs, will be generated and reported accordingly.

The effect of MLN9708 on immune effector cells after allogeneic stem cell transplant will be analyzed by examining the difference in the actual change from baseline at Cycle 1 Day 4, Cycle 1 Day 8, Cycle 1 Day 15, and Cycle 2 Day 1, and the percentage change from baseline at Cycle 1 Day 4, Cycle 1 Day 8, Cycle 1 Day 15, and Cycle 2 Day 1, among those patients participating in the biomarker research component. Each analysis will be performed within dose level and total patients.

The following parameters will be examined:

- CD3+, CD4+, CD8+, CD45+, CD19+ and CD56+/CD16+ cell counts, by fluorescence-activated cell sorting
- Regulatory T cell counts by intracellular staining of FoxP3, and surface staining of CD4+ and CD25+ cells
- Inflammatory cytokine concentrations of IL-1 β , IL-6, IL-8, IL-10 and TNF- α .

CONFIDENTIAL

STUDY DRUG: MLN9708

SCRI INNOVATIONS STUDY NUMBER: MM 42

FINAL PROTOCOL: 11 APRIL 2014

AMENDMENT NUMBER 3: 11 FEBRUARY 2016

VERSION 4

For each parameter, the actual change from baseline and the percentage change from baseline, at each time point, will be analyzed using the two-sided Wilcoxon signed-rank procedure to test whether either the change is statistically different from zero.

The significance level will be set at 10%, and there will be no adjustment to the alpha level for multiple comparisons. The rationale for the reporting of p-values in these analyses is for hypothesis-generating purposes only.

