
Correlative Testing:
	
Immune analysis from the peripheral blood will include:
 
 • CD3+, CD4+, CD8+, CD45+, CD19+ and CD56+/CD16+ cells by fluorescence-activated cell sorting • Regulatory T cells by intracellular staining of FoxP3 and surface staining of CD4+ and CD25+ cells • Inflammatory cytokines including IL-1β, IL-6, IL-8, IL-10 and TNF-α 
Participating sites will process the samples, analyse and report data for the flow cytometric analysis. Samples for cytokine analysis will be shipped to a central laboratory for analysis. Samples will be collected on Days 1 (pre-dose), 4, 8, and 15 of Cycle 1 and Day 1 (pre-dose) of Cycle 2 from 3 patients at each dose level and from 5 patients at the MTD/MPD.

CONFIDENTIAL

STUDY DRUG: MLN9708

SCRI INNOVATIONS STUDY NUMBER: MM 42

FINAL PROTOCOL: 11 APRIL 2014

AMENDMENT NUMBER 3: 11 FEBRUARY 2016

VERSION 4

MM 42 PROTOCOL SYNOPSIS

Statistical Methodology:	
Safety of MLN9708 when used in this indication (primary endpoint) will be evaluated as follows. Toxicity profile data will include adverse events (AEs), laboratory parameters, vital signs, and other protocol-specified tests that are deemed critical to the safety evaluation. Safety data will be tabulated for all patients who receive any amount of study medication. Adverse events will be tabulated by system organ class, preferred term, severity, and relation to treatment. The tabulation of laboratory parameters will indicate the normal range of each parameter. Each analyte value will be classified as falling above, below, or within the normal range.
 
Progression-free survival and OS (efficacy secondary endpoints) estimates will be generated using Kaplan-Meier methods, both for all patients enrolled and those patients receiving the MTD. Two-year PFS and OS estimates with 95% confidence intervals (CIs), and median PFS and OS with 95% CIs, will be generated and reported accordingly.
 
Incidence of GVHD (safety secondary endpoint) will reported in a manner consistent with the AE reporting previously described.
 
Demographic data and baseline disease characteristics will be summarized using descriptive statistics.
 
All statistical analyses will be performed using SAS 9.3 or the current version of SAS available at the time of analysis.

---------------------------------	--

MM 42 CONTACT INFORMATION

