5.5 Correlative Studies

For patients who participate in the exploratory biomarker research component of this study, peripheral blood samples will be collected on Days 1 (pre-dose), 4, 8, and 15 of Cycle 1 and Day 1 (pre-dose) of Cycle 2. Participating patients will include 3 patients at each dose level and 5 additional patients at the MTD.

Immune analysis from the peripheral blood will include:

- CD3+, CD4+, CD8+, CD45+, CD19+ and CD56+/CD16+ cells by fluorescence-activated cell sorting
- Regulatory T cells by intracellular staining of FoxP3 and surface staining of CD4+ and CD25+ cells
- Inflammatory cytokines including IL-1 β , IL-6, IL-8, IL-10 and TNF- α

Participating sites will process the samples, analyse them, and report data for the flow cytometric analysis. Samples for cytokine analysis will be shipped to a central laboratory for analysis. For shipment, handling, etc. of the correlative testing blood samples blood, see the Study Manual.

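### In the pooled biomarker analysis, and less so at the MTD, the signed-rank test on percentage change favours increases and has less power for decreases

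*Protocol*

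**What the plan says.** The effect of MLN9708 on immune effector cells is a secondary objective (Protocol Section 2.2; SAP Section 1.1). Protocol Section 10.4.2 compares four time points with baseline (Cycle 1 Days 4, 8 and 15, and Cycle 2 Day 1) for each cell count and cytokine. It says that "the actual change from baseline and the percentage change from baseline, at each time point, will be analyzed using the two-sided Wilcoxon signed-rank procedure", with zero change as the null on both scales. On grouping it says: "Each analysis will be performed within dose level and total patients". On error control: "The significance level will be set at 10%, and there will be no adjustment to the alpha level for multiple comparisons". On purpose: "The rationale for the reporting of p-values in these analyses is for hypothesis-generating purposes only".

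The number of patients is stated in two ways. Section 5.5 says: "Participating patients will include 3 patients at each dose level and 5 additional patients at the MTD". The synopsis says samples come "from 3 patients at each dose level and from 5 patients at the MTD/MPD", which can also be read as 5 in total at that dose.

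Neither the Protocol nor the SAP text supplied names a log scale, a symmetry condition, a variability figure or a rule for zero or undetectable values in this analysis. The SAP lists the objective but adds no method for it.

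**The concern.** The signed-rank test ranks the absolute changes and compares the rank sums of the rises and falls. Its null distribution assumes that, without an effect, a change of a given size is equally likely in either direction. Percentage change is bounded at -100% below and unbounded above, so it cannot satisfy this when baseline and follow-up are exchangeable. The large ranks go mainly to increases.

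The stake is directional. A two-sided p-value is read as even-handed, yet chance findings here would be mostly apparent increases, and real falls would be harder to detect. Section 1.2.8 expects proteasome inhibition to reduce GVHD, so falls in inflammatory cytokines are of interest. A hypothesis-generating label excuses multiplicity and imprecision. It does not remove a bias in which hypotheses are generated.

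**Working it through.** **Inputs from the documents**
- Level: 10%, two-sided (Section 10.4.2).
- Dose levels: 3 (Section 5).
- Group sizes under Section 5.5: 3 at each of two levels, 3 + 5 = 8 at the MTD, pooled 3 × 3 + 5 = 14.
- Group sizes under the other synopsis reading: 3, 3 and 5, pooled 11. Section 5.5 also gives 11 pooled if only two levels open (3 + 3 + 5).
- Parameters: 6 cell populations + regulatory T cells + 5 cytokines = 12.

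**Assumptions**
- The within-patient SD of log(post/baseline), s, is ranged from 0.3 to 1.0, because the documents give none. One SD is then a factor of e^0.3 = 1.35 to e^1.0 = 2.7.
- Values are lognormal and, with no effect, baseline and follow-up are exchangeable.
- The between-patient log SD is 0.6. It matters only for the actual-change test.

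**1. The level the plan would reach if changes were symmetric.** From the exact null distribution, the largest attainable two-sided level not above 10% is:
- n=3: none. The smallest p is 2/2³ = 0.25.
- n=5: 2/2⁵ = 6.25%, reached only when all five signs agree.
- n=8: 7.8%.
- n=11: 8.3%.
- n=14: 9.06%.

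At n=3 nothing can be rejected. At n=5 only the signs matter, and these are the same on every scale, so skewness has no effect.

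**2. Direction of the tilt.** For a ratio r > 1, the rise scores r - 1. Its mirror image 1/r scores a fall of 1 - 1/r = (r - 1)/r. The rise is larger by the factor r. This needs only exchangeable positive values. The lognormal model sets the size of the tilt, not its direction.

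**3. Size under no effect.** Exact test on percentage change, simulated; entries are false increases / false decreases, with the total in brackets, in %. Repeat runs move entries by up to about 0.3 points.

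| s | n=8 | n=11 | n=14 |
|---|---|---|---|
| 0.3 | 4.9 / 3.1 (8.0) | 5.8 / 3.1 (8.9) | 6.9 / 3.1 (10.0) |
| 0.5 | 5.6 / 2.8 (8.4) | 7.1 / 2.6 (9.7) | 8.7 / 2.4 (11.1) |
| 0.7 | 6.4 / 2.5 (8.9) | 8.4 / 2.2 (10.6) | 10.5 / 2.0 (12.5) |
| 1.0 | 7.6 / 2.2 (9.8) | 10.3 / 1.8 (12.1) | 13.3 / 1.5 (14.8) |

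On the log ratio the tails are equal at every s: about 3.9% each at n=8 and 4.5% each at n=14. Actual change also has equal tails, with a total of about 7.8% at n=8 and 9.0% at n=14.

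**4. Power for a true halving.**

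| n, s | Percentage change | Log ratio | Actual change |
|---|---|---|---|
| 14, 0.5 | 99% | 99.9% | 99.6% |
| 14, 0.7 | 84% | 96% | 93–94% |
| 14, 1.0 | 47% | 76% | 70–72% |
| 8, 0.7 | 60% | 75% | 70% |
| 8, 1.0 | 32% | 48% | 44% |

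The ranges for actual change are the spread across separate simulations.

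**5. How many tests.** With all three levels open, percentage change is tested 12 parameters × 4 times × 4 groups = 192 times. The two 3-patient groups account for 12 × 4 × 2 = 96, which cannot reject. That leaves at most 96: 48 at the MTD and 48 pooled. If the MTD group has 5 patients, only the 48 pooled tests are touched.

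**The case against.** A reader might infer that the analysis is invalid at its stated 10% level. The documents do not support that. They give no variability, and over the assumed range the total passes 10% only in the pooled group. It does so at 14 patients once s exceeds roughly 0.3 to 0.5, and at 11 once s exceeds roughly 0.5 to 0.7. At 8 patients it stays below 10% throughout; it would take s of about 1.5 to reach 10.9%.

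A reader might also infer that the plan misses decreases. The same sentence of Section 10.4.2 tests actual change, which keeps its level. For a halving at n=14 it comes within about 3 points of the log ratio at s=0.7 and within about 6 at s=1.0. The lost power belongs to the percentage-change p-values, not to the plan as a whole, and it is negligible at s=0.5.

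Two further limits are fair. Section 5.5 calls the biomarker work exploratory, no decision is tied to these p-values, and hundreds of unadjusted tests at 10% will give chance positives on any scale. The replacement also has a price: a log ratio fails if either value is zero, whereas percentage change fails only at a zero baseline. That such values will occur is possible, but nothing in the documents shows it.

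What stands is the tilt. It follows from the scale itself, and the actual-change test does not correct the percentage-change p-values reported beside it.

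**Conclusion.** The point holds in a limited form. In the pooled analysis (14 patients, or 11 on the other reading), and less so in an 8-patient MTD cohort, the signed-rank test on percentage change is tilted toward increases and has less power for decreases. For s from 0.3 to 1.0 the total false-positive rate is about 10% to 15% at n=14 and about 9% to 12% at n=11. At n=8 it is below 10%, with tails from 4.9/3.1% to 7.6/2.2%. Groups of 3 or 5 are unaffected, so at most 96 of the 192 percentage-change tests are involved. The direction does not depend on the lognormal model. The sizes do, and they depend on an SD that the documents do not give. Because the p-values are hypothesis-generating and a sound test on actual change sits alongside, this is a low-priority correction.

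**What to change.** In Protocol Section 10.4.2, replace the signed-rank test on percentage change with the same test on log(post/baseline). Report the median or geometric mean ratio with a confidence interval, and keep percentage change as a descriptive column. The actual-change test can stay. Carry the sentence into the SAP, whose supplied text has no method for this objective. At the same time reconcile the synopsis with Section 5.5 on the number of biomarker patients at the MTD, since this decides whether that group has 5 or 8.

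The change needs no new data or patients, but it is not free:
- A fill-in value must be stated in advance for a zero or undetectable measurement at either time, for example a fixed fraction of the assay limit. The choice is arbitrary, and pairs undetectable at both times become zero differences.
- Nominal power for increases falls. For a doubling at n=14 and s=1.0 it goes from 89% to 76%. The higher figure comes with a false-increase rate of about 13% instead of 4.5%.
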